6.11.2 Secondary Efficacy Endpoints

Secondary endpoints will be summarized with descriptive statistics, and as appropriate, comparisons with t-test or ANCOVA, or non-parametric methods if assumptions of normality are not met. Pubertal staging will be with categorical methods showing count and %. The change from baseline for the secondary endpoints will also be presented. For any comparisons performed, the null hypothesis for the test is that the two groups are equal at $p < 0.05$. There is no intent to show non-inferiority for the secondary endpoints, as the sample size was not determined to be sufficient to show non-inferiority for these secondary endpoints.

The main intent of ANCOVA will be to explore the influence of the covariates on the outcome of the secondary endpoint. Differences between treatment groups are not expected,

so there is no plan to adjust the alpha level of each comparison. The primary covariates will be those used for the primary endpoint, plus the baseline value of the secondary endpoint being analyzed.

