9.3 Analysis Populations

9.3.1 *Safety Population*

The safety population will consist of all subjects completing a screening evaluation and receiving any amount of study drug.

9.3.2 *PK/PD Population*

The PK/PD analysis population will consist of all subjects receiving study drug and having at least one post-treatment PK/PD assessment. A PK/PD per protocol subset will include all subjects with complete PK/PD assessments and no missed doses in the dosing interval prior to a PK/PD assessment.

9.3.3 *Intent-to-Treat Population*

The intention to treat analysis (ITT) will be the primary analysis population. The ITT population will consist of all subjects completing at least one month of dosing with completed efficacy assessments at the Month 1 Visit. For subjects completing less than the 12 months of treatment, the height velocity at 12 months will be imputed from the change from baseline of last measurement of HT-SDS. With this procedure, a 12 month height velocity measurement will be available for all subjects in the ITT.

Baseline characteristics of the excluded subjects will be reported. In the event that numerous imputations are required, comparisons of subject that completed versus those who dropped and required imputation will be done.

9.3.4 *Per Protocol Population*

A per protocol analysis will be used to evaluate efficacy parameters. All subjects completing one year of continuous study dosing with efficacy assessments at Month 12 will be included. Patients with major dosing deviations ($\geq 10\%$ of total assigned doses missed) will be excluded from per protocol analysis. Missing data for the per protocol population will not be imputed.

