1. INTRODUCTION/BACKGROUND

This statistical analysis plan (SAP) describes the data analysis specifications for Protocol 14VR4 entitled “Comparison of Somavaratan (VRS-317), a Long-acting Human Growth Hormone, to Daily rhGH in a Phase 3, Randomized, One-year, Open-label, Multi-center, Non-inferiority Trial in Pre-pubertal Children with Growth Hormone Deficiency,” Version 4, 5 April 2017.

This SAP follows the International Conference on Harmonisation (ICH) Guidelines E3 and E9. All statistical analyses will be performed using SAS[®], Version 9.4 or higher. In cases in which the analyses in this SAP differ from those in the study protocol, the analyses in the SAP supersede those in the protocol. Should differences exist, these will be described in Section 6.2 of this document.

This protocol is a randomized, multi-center, open-label, non-inferiority study for pre-pubertal naïve to treatment children with growth hormone deficiency (GHD). Subjects will be randomized to receive 3.5 mg/kg somavaratan twice-monthly or daily treatment with rhGH. Safety and efficacy of these treatments over the course of one year will be evaluated along with changes in pharmacodynamic responses (IGF-I, IGF binding protein-3 (IGFBP-3), growth hormone binding protein (GHBP) and acid labile subunit (ALS)), bone age, weight, body mass index (BMI), height standard deviation scores (HT-SDS), and anti-drug antibody (ADA) responses.

Somavaratan is a fusion protein consisting of recombinant human growth hormone (rhGH) and two sequences (XTEN) of hydrophilic amino acids, designed to maintain active drug levels for a longer period of time than currently available therapies. It is being developed for treatment of GHD in adults and children and as a long-acting alternative to daily rhGH injections, which is currently the only approved treatment in the United States for adults and children with growth hormone deficiency.

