5.2 SECONDARY ENDPOINTS

The following secondary efficacy endpoints will be analyzed in hierarchical order:

- Change in height SDS (Height SDS based on Center for Disease Control (CDC) Clinical Growth Charts; 2000)
- Change in bone age relative to chronological age (BA/CA)
- Change in Body Mass Index
- Change in body weight

IGF-I and IGFBP-3 responses to study drug administration and their relationship to height velocity will be evaluated.

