6.4 HANDLING OF MISSING VALUES AND OUTLIERS

Because of subject privacy limitations, birth dates may only be reported by month and year in certain locations. Where the specific birth day is not available, the day of month will be imputed as the 15th.

For the primary endpoint in the ITT population, missing height at 12 months will be imputed from the last available height. This imputation assumes no growth after the last available measurement observed at study exit. This is an extremely conservative approach. For example, a █ year old █ subject who discontinued at month 6 with annualized HV of 6 cm/yr (Day 1 height of █ cm and Month 6 height of █) will have the height at 12 months imputed to █ cm, resulting in an annual HV of 3 cm/yr.

For the sensitivity analysis of the effect of missing data on the primary endpoint, height velocity at Month 12, a tipping point approach will be used. The missing data will be imputed as follows:

For the control group:

1. All subjects to the control group mean (calculated without subjects missing endpoint)
2. 50% to the group mean, 50% to the HV associated with each subjects last reported height (no additional gain in height)
3. Each subject's HV imputed based on its own last reported height

For the somavaratan group:

1. All subjects to the somavaratan group mean (calculated without subjects missing endpoint)
2. 50% to the group mean, 50% to the HV associated with each subjects last reported height (no additional gain in height)
3. Each subject's HV based on its own last reported height
4. Each subject imputed to HV based on last reported height, minus 1 cm.
5. Each subject imputed to HV based on last reported height, minus 2 cm (the non-inferiority margin, to avoid imputing to a common mean).

The reduction of the imputed HV by -1 and -2 cm will be limited to a minimum 0 HV, as negative HV is not possible. This will result in a total of 15 comparisons which should cover the range of plausible results for the subjects who are not able to provide Month 12 height velocity, and accounts for combinations where the somavaratan drop outs will have worse outcomes than drop outs in the control group (e.g., control group imputation 1 versus somavaratan imputations 2 to 5).

No imputations will be considered for the PP populations.

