6.5.2 Stopping Rules

The Stopping Criteria for individual subjects include:

- The Principal Investigator and/or Medical Monitor conclude it is unsafe for the subject to continue.
- A new diagnosis of a significant medical condition or initiation of a new treatment if such condition or new treatment can influence the response to study drug (e.g., diabetes, renal failure).
- Individual subjects with a change in HT-SDS ≤ 0 in the past 6 months may be withdrawn from treatment at the discretion of the PI and Medical Monitor.
- For individual subjects with 2 consecutive IGF-I SDS ≥ 3.0 , the PI and Medical Monitor will determine if the subject may proceed with a dose reduction or be removed from the study.

The Stopping Criteria for the somavaratan treatment arm include:

- The determination is made that it is unsafe to continue because of unexpected adverse events.
- A high frequency or unusual severity of expected events such as intracranial hypertension (IH), slipped capital femoral epiphyses (SCFE), progression of scoliosis or other.

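### Only the primary endpoint has a rule for children who leave before Month 12, so an observed-data comparison of change in height SDS can modestly understate a somavaratan deficit

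*SAP*

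**What the plan says.** **Missing data.** SAP 6.4 sets its main rule for one endpoint: "For the primary endpoint in the ITT population, missing height at 12 months will be imputed from the last available height". The sensitivity analysis is limited in the same way, in a sentence beginning "For the sensitivity analysis of the effect of missing data on the primary endpoint, height velocity at Month 12, a tipping point approach will be". For the per-protocol set the SAP states: "No imputations will be considered for the PP populations".

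Protocol 9.1 and 9.3.3 carry the last height SDS forward, but only to obtain a height velocity: "With this procedure, a 12 month height velocity measurement will be available for all subjects in the ITT". SAP section 1 adds that "the analyses in the SAP supersede those in the protocol". The list of changes from the protocol in SAP 6.2 says nothing about missing secondary values.

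**Secondary endpoints.** SAP 5.2 puts change in height SDS first in a hierarchical list, ahead of BA/CA, BMI and weight. SAP 6.11.2 gives the method: "Secondary endpoints will be summarized with descriptive statistics, and as appropriate, comparisons with t-test or ANCOVA". Non-parametric tests are the fallback when normality fails. No repeated-measures model is named. SAP 6.11 assigns analysis sets to the primary efficacy analyses only.

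**Withdrawal.** SAP 6.5.2 and Protocol 3.5.2.1 list this among the individual stopping criteria: "Individual subjects with a change in HT-SDS ≤ 0 in the past 6 months may be withdrawn from treatment". The decision is left to the PI and Medical Monitor. The lead-in sentence of Protocol 3.5.2.1 speaks instead of withdrawal from the study.

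**Exit visit.** Protocol 4.4 and 7.3 ask early leavers to have the Month 12 procedures. Neither document says whether an exit value counts as the Month 12 value of a secondary endpoint.

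**The concern.** A t-test or ANCOVA on change at Month 12 uses only children who have a value. With no rule for the others, two routes are open. They can drop out of the comparison, or their exit values can be pooled with true 12-month changes, although they reflect a shorter time on treatment.

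Dropping them is not neutral for height SDS, because the discretionary criterion acts on that same variable. If somavaratan children grow less well, more of them meet the criterion and more may leave. The remaining somavaratan mean is then raised by more than the rhGH mean, and the deficit shrinks.

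Height is measured at Months 1, 3, 6, 9 and 12, so the values that trigger withdrawal are already in the database. An ANCOVA at Month 12 alone does not use them. At stake is the estimate and interval for the first-listed secondary endpoint. The non-inferiority result is not at stake.

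**Working it through.** **The plan's own figures.** 76 + 8 = 84, so the drop-out allowance is 8/84 = 9.5%. At 3:1, 84 children are 63 somavaratan and 21 rhGH. The documents give no mean or SD for change in height SDS, so there is no plan figure for that endpoint to reproduce.

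**Inputs from the documents.** Height-velocity SD up to 3.0 cm/yr (SAP 3.5). rhGH mean 10.25 cm/yr, the middle of the 9.5 to 11 in Protocol section 1. Margin 2 cm/yr.

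**Assumed.** Reference growth R of 5 to 6 cm/yr; height SD 5 cm; correlation r between half-year growths of 0.6 to 0.8; the criterion applied once, at Month 6; a share p of those meeting it withdrawn. The height SD rescales the true difference, the bias and the SE alike, so it does not affect the percentages.

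**Formulas**, for an arm with mean velocity m and velocity SD σ:

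- Half-year SD: s = σ / √(2(1 + r))
- Share meeting the criterion: q = Φ(z), with z = (R/2 − m/2)/s
- Upward shift of the observed mean: p(1 + r)s·φ(z) / [(1 − pq) × 5] SDS
- Bias in the difference: somavaratan shift minus rhGH shift

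**Somavaratan 2 cm/yr worse; σ = 3.0, R = 6, r = 0.8, p = 0.5**

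- s = 3/√3.6 = 1.581
- rhGH: z = (3 − 5.125)/1.581 = −1.344, q = 8.9%, shift 0.048
- Somavaratan: z = (3 − 4.125)/1.581 = −0.712, q = 23.8%, shift 0.100
- True difference: −2/5 = −0.40
- Observed difference: −0.40 + (0.100 − 0.048) = −0.348
- Withdrawals: 0.5 × (63 × 0.238 + 21 × 0.089) = 8.4
- SE: (3/5)√(1/63 + 1/21) = 0.151, so the bias is 0.052/0.151 = 0.34 SE

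**Range** (r = 0.6 to 0.8 throughout)

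| True deficit | σ, R | p | Withdrawn of 84 | True | Observed | Bias |
|---|---|---|---|---|---|---|
| 2 cm/yr | 3.0, 6 | 0.5 | 8.4 to 9.0 | −0.40 | −0.35 | 12 to 13%, 0.31 to 0.34 SE |
| 2 cm/yr | 2.0, 5 | 0.5 | 2.0 to 2.4 | −0.40 | −0.38 | 5%, about 0.2 SE |
| 1 cm/yr | 3.0, 6 | 0.5 | 5.7 to 6.3 | −0.20 | −0.18 | 0.02 SDS |
| 0.5 cm/yr | 3.0, 6 | 0.5 | 4.7 to 5.2 | −0.10 | −0.09 | 0.01 SDS |
| 0 | 3.0, 6 | 0.5 | 3.8 to 4.3 | 0 | 0 | 0 |
| 2 cm/yr | 3.0, 6 | 1 | 16.9 to 18.0 | −0.40 | −0.27 to −0.28 | 30 to 33% |

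With p = 0.5, other combinations of σ from 2.0 to 3.0 and R from 5 to 6 fall between the first two rows in percentage terms. The ratio to the SE stays below 0.4, because a smaller σ also gives a smaller SE.

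**Does using earlier heights help?** In 4,000 simulated trials per scenario at 63/21, adjusting for the Month 6 change in height SDS (the two-visit equivalent of a repeated-measures model) recovers −0.40 in the 2 cm/yr scenario. The SE is 0.15 to 0.16, against 0.15 with complete data.

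**The case against.** The strongest reply is that little rests on these tests. SAP 6.11.2 disclaims any intent to show non-inferiority on the secondary endpoints and describes the ANCOVA as mainly exploring covariates. SAP 6.6 calls additional comparisons exploratory. This stands and limits the importance of the point. It does not remove it, because SAP 5.2 ranks the endpoints and SAP 6.11.2 still names a p < 0.05 test.

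Four stronger readings are tempting, and the documents do not support them.

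- **The deficit could shrink by a third.** That requires withdrawing every child who meets the criterion, 17 to 18 of 84, against an allowance of 8. Even the half-withdrawn case spends the whole allowance on one criterion.
- **A diluted height-SDS result would wrongly back up a successful primary.** The 2 cm/yr scenario sits at the non-inferiority margin. In simulation, with an unadjusted t-test and the SAP 6.4 imputation, the primary then passes in about 1% of trials at one-sided 0.025 and 2 to 3% at 0.05. With half withdrawn, the observed-data height-SDS comparison is still significantly negative in about two thirds of trials. At a 0.5 cm/yr deficit the primary passes more often (33 to 54%), but with half withdrawn the bias is only about 0.01 SDS.
- **The criterion removes every poor grower.** It is discretionary, its window is the past 6 months, and the endpoint is change from baseline.
- **The plan prescribes completers only.** It is silent. Exit values may exist, and using them as Month 12 values is the other possibility. That route has not been sized here.

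No size is shown for weight, BMI or BA/CA.

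**Conclusion.** The gap is real and of modest size. Neither document says how a child without a Month 12 value enters the secondary comparisons, and the stated methods can lose the lowest height-SDS values. With half of those meeting the criterion withdrawn, and the assumed reference growth, height SD and half-year correlation, a true −0.40 SDS is estimated as −0.35 to −0.38. The bias is below 0.03 SDS for deficits of 0.5 to 1 cm/yr and zero when the arms are equal. Its direction and size depend on unequal withdrawal between arms, which the documents do not quantify.

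The non-inferiority conclusion does not depend on this. The change is still worth making before database lock: treatment is open-label, the choice is otherwise left open, and the better method uses data already collected.

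**What to change.** In SAP 6.11.2:

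- Analyse change in height SDS in all randomised subjects with a mixed model for repeated measures over Months 1, 3, 6, 9 and 12, with treatment by visit, the baseline value and the primary-model factors. Report the Month 12 difference with its 95% CI.
- Use the same model for weight and BMI, for consistency.
- State that exit assessments enter at their actual time and not as Month 12 values.
- Keep BA/CA, measured only at screening and Month 12, as an observed-data analysis, with exit X-rays listed separately.

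Separately, reconcile the passages in Protocol 3.5.2.1 and SAP 6.5.2 on whether the height-SDS criterion means leaving treatment or leaving the study. The answer decides whether later heights can exist for these children.

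The cost is SAP wording and one standard model, with no new data and almost no loss of precision. The downside is a missing-at-random assumption. It fits withdrawal driven by recorded height SDS and is weaker than what the observed-data ANCOVA needs, but it could fail where the discretionary decision rests on information not recorded.

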6.12 PHARMACOKINETIC AND PHARMACODYNAMIC ANALYSES

6.12.1 Pharmacokinetic Analyses

Calculation of PK parameters and the PK analysis and interpretation will be presented in a separate report.

6.12.2 Pharmacodynamic Analyses

IGF I and IGF I SDS.

The peak and trough levels of IGF I and IGF SDS will be summarized by each time point sampled. The change from baseline to last peak and last trough level will be calculated and summarized.

An exploratory analysis of the relationship of IGF-I, IGF SDS and IGFBP-3 to height velocity will be done with ANCOVA. The model used for the primary endpoint will be the starting point, with IGF results added.

The molar ratio between IGF-I and IGFBP-3 will be calculated and summarized over time. A molecular mass of 7,649 Da (Daltons) will be used for IGF-I and a molecular mass of 43,000 Da (Daltons) will be used for IGFBP-3. Assuming 1 Da equals 1 g/mole, then the molarity of IGF-I and IGFBP-3, respectively, will be calculated using the following formulas:

$$\text{Molarity of IGF - I} \left(\frac{\text{nmol}}{\text{mL}} \right) = \frac{\text{IGF - I value in } \frac{\text{ng}}{\text{ml}}}{7,649}$$

and

$$\text{Molarity of IGFBP - 3} \left(\frac{\text{nmol}}{\text{mL}} \right) = \frac{\left(\text{IGFBP - 3 value in } \frac{\text{mg}}{\text{L}} \right) * 1000}{43,000}$$

Once derived, the molar ratio will be calculated by dividing the moles of IGF-I by the moles of IGFBP-3.

6.12.3 Immunogenicity/Antibodies

Immunogenicity of somavaratan and daily rhGH will be assessed by measurement of anti-drug antibodies (ADAs) in serum samples. ADAs to both somavaratan and daily rhGH will be determined following a tiered approach consisting of screen, confirmation, titration and additional characterization. The additional characterization of somavaratan ADAs includes measurement of ADA specificity to rhGH and XTEN and neutralization capacity in an *in*

vitro cell bioassay. A summary of the ADA results will be described in detail in a separate immunogenicity analysis report included in the Integrated Summary of Immunogenicity (ISI).

The effect of ADAs on height velocity (HV) and safety will be evaluated for both treatment groups. An analysis of variance (ANOVA) model of HV as dependent variable with treatment and ADA classification (e.g., positive/negative status (c.f., Shankar et al., 2014); based on titer, etc.) as factors will be used as the first step in this evaluation. Comparisons of somavaratan PK, IGF-I and IGF-SDS between the ADA classification groups will also be performed. The additional characterization data will also be assessed for relevance to HV.

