3.2 Rationale for Study Design and Control Group

There are currently no preventative treatments for GHD in children or adults. The only approved treatment is daily rhGH. Somavaratan is initially being developed for twice-monthly dosing in GHD children to provide a simpler alternative than daily dosing that may avoid the compliance problems and attendant loss of treatment effect seen with daily rhGH therapy. Accordingly, the pivotal trial for somavaratan is a direct comparison to daily rhGH using a non-inferiority test of hypothesis. Age and IGF-I SDS at baseline are known to affect the primary efficacy endpoint (height velocity). Therefore, subjects will be randomized to receive either somavaratan or daily rhGH. The treatment arms will be balanced for baseline age and IGF-I SDS.

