6.11.1 Primary Efficacy Endpoint

Annual height velocity will be calculated using the formula below:

$$\begin{aligned} \text{Height Velocity} \left(\frac{\text{cm}}{\text{year}} \right) \\ = \left[\frac{\text{Month X Height (cm)} - \text{Baseline Height (cm)}}{\text{Month X date} - \text{Baseline date}} \right] * 365.25 \end{aligned}$$

The primary analysis will be the comparison of the annual height velocity between somavaratan and daily rhGH, with null hypothesis that the difference is less than or equal to -2 cm/year, the non-inferiority margin. An Analysis of Covariance (ANCOVA) model will be used to determine the adjusted (least squares) means and SE to determine the confidence interval (CI) of the difference. The model fixed effects are treatment group, region and gender, with baseline age, baseline IGF-I SDS, and baseline height as covariates. The ANCOVA is used to adjust for the influence of these covariates, and not to determine if these covariates themselves are statistically significant factors. A reduced model removing covariates with $p > 0.10$ may also be considered for exploratory purposes. The randomization stratification should result in balance between the two treatments in terms of the factors. Levene's will be used to determine if the variances is equal between the two treatment groups. If there is evidence of unequal variance, a Welch test on the treatment main effects will be performed with null hypothesis of somavaratan HV - daily rGH HV ≤ -2 cm. Rejection of this null hypothesis will be evidence of non-inferiority of somavaratan to daily rGH.

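### The first-step model for antibody effects on height velocity leaves out the baseline covariates the plan uses elsewhere for the same outcome, and does not say whether the effect is estimated by arm

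*SAP*

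**What the plan says.** SAP 6.12.3 sets the scope: "The effect of ADAs on height velocity (HV) and safety will be evaluated for both treatment groups". The one model it names for HV is "An analysis of variance (ANOVA) model of HV as dependent variable with treatment and ADA classification" "as factors will be used as the first step in this evaluation". It mentions neither covariates nor an interaction.

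The same section shows that the antibodies are not alike in the two arms: "The additional characterization of somavaratan ADAs includes measurement of ADA specificity to rhGH and XTEN and neutralization capacity". It adds that "The additional characterization data will also be assessed for relevance to HV", without giving a method.

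Elsewhere HV is handled differently. Protocol 3.2 states: "Age and IGF-I SDS at baseline are known to affect the primary efficacy endpoint (height velocity". For the primary analysis, SAP 6.11.1 says: "The model fixed effects are treatment group, region and gender, with baseline age, baseline IGF-I SDS, and baseline height as covariates". SAP 6.12.2 builds the exploratory analysis of IGF-I and IGFBP-3 against HV on that same primary model.

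On status, SAP 2.2 asks only that the presence of ADA be determined and responses explored. The Protocol synopsis calls the ADA-to-HV link exploratory, and Protocol 9.9 places it among the other analyses.

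**The concern.** Children who develop antibodies may differ at baseline from those who do not. Randomisation is stratified by region, age and IGF-I SDS (SAP 3.6), but that balances the treatment arms and not the ADA groups. If ADA-positive children are younger, or start with lower IGF-I SDS, a crude comparison mixes that difference with any antibody effect. Leaving out known predictors of HV also leaves their variance in the error term. The covariates are already collected and are used in the analysis described one subsection earlier.

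A second gap concerns what is being estimated. With treatment and ADA as main effects only, the model returns one ADA coefficient for both drugs. For a new fusion protein, the question of interest is the ADA difference within the somavaratan arm. The shared coefficient answers that only if the effect is the same in both arms or if no rhGH child is ADA positive.

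At stake is how the immunogenicity findings are read, not the non-inferiority conclusion.

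**Working it through.** **Inputs from the documents.** SD of annual HV 3.0 cm/yr (Protocol 9.2, SAP 3.5); allocation 3:1; planned total 84, hence 63 somavaratan and 21 rhGH; maximum 102 and 34 (Protocol 4.1).

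**Inputs that are assumptions.** ADA prevalence, the share of HV variance explained by covariates (R²), the slope of HV on age, and any age gap between ADA groups. The documents give none of these. ADA is treated as positive or negative.

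**The plan's own figure.** The plan gives no figure for the ADA analysis. The SD and arm sizes come from the primary calculation. With margin 2.0, SD 3.0, true difference 0, one-sided alpha 0.05 and 80% power (power is not stated, so assumed), the rhGH arm needs (1 + 1/3) × (1.645 + 0.842)² × 3.0² / 2.0² = 18.6, so 19. The somavaratan arm needs 57, and the total is 76, as stated.

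**1. Noise from omitted covariates.** If the covariates are roughly unrelated to ADA status, adjustment multiplies the standard error (SE) by √(1 − R²).

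| R² | SE multiplier | Unadjusted SE relative to adjusted |
|---|---|---|
| 0.10 | 0.949 | 1.05 |
| 0.20 | 0.894 | 1.12 |
| 0.30 | 0.837 | 1.20 |

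**2. Confounding.** For one covariate, bias = HV slope × covariate gap between ADA groups. If HV falls by 0.2 to 0.5 cm/yr per year of age and the groups differ by 1 year, the bias is 0.2 to 0.5 cm/yr. It masks an antibody effect if ADA-positive children are younger, and exaggerates it if they are older.

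**3. Averaging over two drugs.** In the main-effects model, the weight on the somavaratan ADA effect is w = n_s p_s(1 − p_s) / [n_s p_s(1 − p_s) + n_c p_c(1 − p_c)], where p is the ADA-positive share in each arm. An effect confined to somavaratan is estimated at w times its size. At 3:1:

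| ADA positive, somavaratan / rhGH | w | Dilution |
|---|---|---|
| any / 0% | 1.00 | none |
| 30% / 10% | 0.875 | 12.5% |
| 50% / 30% | 0.78 | 22% |
| equal | 0.75 | 25% |
| 80% / 50% | 0.66 | 34% |
| 10% / 50% | 0.52 | 48% |

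A simulation of 4,000 trials at 102/34 with 51 and 10 children ADA positive, and a true effect of −2.0 cm/yr in somavaratan only, gave −1.57 from the main-effects model and −2.00 with a treatment-by-ADA term. The formula gives w = 0.783, so −1.57.

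**4. Price of estimating by arm.** At 63/21 with 50% positive in both arms:
- Pooled SE = 3.0 / √(15.75 + 5.25) = 0.65 cm/yr.
- Somavaratan-arm SE = 3.0 / √15.75 = 0.76 cm/yr, about 15% larger.
- Covariates must explain 25% of variance before the adjusted by-arm SE matches the unadjusted pooled SE, since 1 − 0.25 = 15.75/21.

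Which estimate is more sensitive depends on the truth. At 102/34 with 30% positive in both arms and two-sided alpha 0.05, a −2.0 cm/yr effect in somavaratan only gives 76% power pooled and 87% by arm. If the same effect exists in both arms, the pooled SE is 3.0 / √28.56 = 0.56 and power is Φ(2.0/0.56 − 1.96), about 95%, against the same 87% by arm.

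**The case against.** The strongest reply is that the SAP calls this model a first step, does not say it is restricted to main effects, and promises evaluation for both groups. It also plans to relate the somavaratan-specific characterization to HV and to compare drug levels and IGF-I across ADA groups. SAP 5.3 leaves room for further covariates in exploratory work. Detailed ADA results go to a separate report that is not among these documents.

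Much of this stands, and it rules out four stronger readings that a reader might infer:

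- *That antibody effect on growth is a listed objective.* The objectives cover ADA responses; their link to HV is exploratory.
- *That the plan definitely fits one common effect.* That is the literal reading, but an interaction is not excluded.
- *That a somavaratan effect will be diluted.* Dilution requires ADA-positive rhGH children and a weaker effect in that arm. The documents establish neither.
- *That pooling makes the estimate noisier.* It lowers the SE, at the risk of bias. Only the missing covariates add avoidable noise.

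The reply does not explain why the named model drops covariates that the protocol regards as predictive and that the adjacent analysis keeps. No second HV model is specified, so covariates and interaction would be chosen after the data are seen.

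**Conclusion.** The point holds as a minor improvement to an exploratory analysis. The omission of covariates is clear from the text and inconsistent with the plan's other HV models. Its cost is an SE about 5 to 20% larger than needed, if R² is 0.1 to 0.3, and confounding whose size and direction cannot be known from the documents. The 0.2 to 0.5 cm/yr above illustrates that bias and does not predict it. Adjustment would remove only the part due to measured factors.

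The averaging over drugs is conditional. It applies only if the model is main effects only. For an effect confined to somavaratan, dilution is zero with no ADA-positive rhGH children and 25% at equal prevalence. It can be larger if the rhGH prevalence is nearer one half than the somavaratan prevalence. Nothing here affects the primary non-inferiority test.

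**What to change.** In SAP 6.12.3, replace the ANOVA with the primary ANCOVA (treatment, region, gender, baseline age, baseline IGF-I SDS, baseline height) plus ADA classification, fitted jointly to both arms. SAP 5.3 makes baseline height conditional while SAP 6.11.1 lists it outright; the ADA model should follow whichever rule governs the primary analysis.

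Also report the somavaratan-arm ADA difference with a 95% CI from a treatment-by-ADA term. If too few rhGH children are ADA positive to support that term, estimate it from the somavaratan arm alone. State the minimum count in advance.

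The cost is one or two sentences and no new data. The by-arm estimate is less precise than the pooled one (0.76 against 0.65 cm/yr in the example above, before any covariate gain), and the rhGH-arm estimate will be imprecise. Separate fully adjusted fits in each arm are not advised, because 21 rhGH children cannot comfortably support five adjustment terms plus ADA.
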